Appendix 3: PAXgene™ Blood for DNA Analysis

**PAXgene™ BLOOD FOR DNA ANALYSIS
SPECIMEN COLLECTION PROCEDURE**

SPECIMEN COLLECTION NOTES*

SCP-124-00

***NOTE:** Refer to protocol flow chart or Specimen Collection Overview Chart for scheduled collection time points.

***NOTE:** Collection of specimens from vascular access devices and heparin or saline locks is not recommended due to the potential for specimen contamination. This specimen should be collected as a peripheral blood draw.

Supplies and Materials (per patient, per time point)

Provided to the Institution

- Requisition form/card
- "PAXgene Blood DNA" labels
- One 8.5 mL PAXgene™ Blood DNA collection tube (Cat#761115)

Precautions

*** SAFETY PRECAUTION:** Contents of the PAXgene™ tube are irritating to skin. Wear disposable gloves, safety glasses or goggles and a laboratory coat and follow standard laboratory safety procedures while working with these tubes. If inhaled, supply fresh air; consult doctor in case of complaints. If skin contact, immediately wash with water and soap, and rinse thoroughly. If contents make eye contact, rinse opened eye for 15 minutes under running water, then consult a doctor. If swallowed, immediately call a doctor.

Required Equipment

- Freezer for -20°C for PAXgene™ tube storage (For storage exceptions/monthly batch shipments).

Labeling

1. Place patient-specific label on the PAXgene Blood DNA tube.
2. If required: Fill out the requisition form/card appropriately (ensure that you follow specific processing instructions per the protocol specific Laboratory Procedure Manual).

Preparation

1. Ensure the patient has signed the appropriate IRB/ERC-approved consent for genetic specimen collection prior to collecting the specimen.
2. Ensure the PAXgene™ Blood DNA collection tubes are at room temperature prior to collecting blood.

***NOTE:** Do not use tubes after the expiration date printed on the label.

3. The PAXgene™ Blood DNA collection tubes should not be the first tubes drawn during venipuncture. **It should be the last tube collected.**

Specimen Collection

1. Collect blood into each PAXgene™ Blood DNA collection tube via your institution's recommended standard procedure for venipuncture.
 - Ensure that the blood has stopped flowing into the tube before removing the tube from the holder.
 - Each tube holds approximately 8.5 mL of blood.
 - Under-filling of the tubes could result in an incorrect blood-to-additive ratio and may lead to poor performance (e.g. poor quality or low quantity)
2. Immediately after collection, completely and gently invert the tube 10 times to mix uniformly.

***NOTE: After each tube is collected, it is CRITICAL to gently invert PAXgene™ 10 times to ensure proper mixing of blood & PAXgene™ proprietary reagent.**

Specimen Processing & Handling

1. Within 5-10 minutes of the blood draw, place tubes upright in a wire or hard plastic rack at ambient temperature (18-25°C).
2. Tubes **must be shipped within 24 hrs of collection** to the laboratory at ambient temperature.

Storage Exceptions (special circumstances only)

If storing specimens for batch shipment: Specimen tubes MUST be transferred to a -20°C freezer, in a wire or hard plastic rack in the upright position, after collection. **Specimen tubes may be stored frozen upright at -20°C for no longer than 4 weeks at -20°C.** Tubes stored at -20°C must be shipped on dry ice to the Laboratory.

***NOTE:** Any storage time and temperature excursions must be documented and communicated upon specimen shipment within the shipment inventory documents.

***NOTE:** Frozen PAXgene™ Blood DNA collection tubes are subject to breakage on impact. To reduce the risk of breakage during handling and shipment, frozen tubes should be treated in the same manner as glass tubes. If freezing is required, a wire or hard plastic rack should be used (**NO STYROFOAM**) as the tubes may crack.

Packaging and Shipping

1. It is the responsibility of the primary investigator to ensure that all staff personnel who will be handling, packaging, and/or shipping clinical specimens are trained and certified as required by National and International regulations and they ship materials in accordance with all current regulations relating to the handling and shipping of hazardous goods.
2. Follow packing and shipping instructions for **AMBIENT** shipments.
3. Contact shipping courier to obtain any required documentation/forms required for shipment.
4. Ship to the Laboratory **within 24 hr of the blood draw.**
5. **Shipping schedule** – Select overnight or priority delivery and ensure that shipments are received at the destination vendor Monday through Friday, except on U.S. holidays. Shipments can be received on Saturday with advanced notification. **Contact the Vendor if you are uncertain about the shipping or receiving schedule.**

9.7 Changes in the Conduct of the Trial

The original protocol dated 22-Mar-2017 [16.1.1.1] was amended on 04-May-2017 [16.1.1.2], 16-May-2017 [16.1.1.3], and 09-Jun-2017 [16.1.1.4]. Amendment 1 was generated to add Part 2 to the study to assess the PK of MK-7264 in subjects with ESRD requiring HD. Amendment 2 was generated to: 1) correct an error in the calculation of the total blood volume in Part 2 and to clarify that blood (pre-dialyzer and post-dialyzer) and dialysate samples were to be collected immediately after HD was stopped and 2) that HD would be approximately 4 hours in duration. Amendment 3 was generated to: 1) correct the blood volume drawn during the study in Part 2 to account for 3 samples per time point during HD; 2) to clarify that the last post-dialyzer blood sample and dialysate sample were to be collected immediately before HD was stopped; 3) to clarify that dialysate samples were to be collected pre-dialysis, post-dialysis, and for 1 minute every 30 minutes during HD for MK-7264 analysis; and 4) to modify the nomenclature of PK parameters calculated on plasma MK-7264 concentrations from the pre- and post-dialyzer lines. A protocol clarification letter (PCL) was issued on 06-Jun-2017 that described the changes outlined in Amendment 3. A second PCL was issued on 27-Jul-2017 to clarify the number of dialysis sessions (2) during the 7-day washout period between MK-7264 dosing in Periods 1 and 2 of Part 2. All 3 amendments were finalized after the initial screening date (14-Apr-2017) but prior to dosing of the ESRD subjects in Part 2 (28 and 29-Jul-2017). The 3 amendments outlined changes that were only relevant for Part 2 of the study; these amendments had no impact on Part 1 of the study that had already begun prior to their finalization. The PCLs were finalized prior to the washout period between Periods 1 and 2 of Part 2. There were no other changes in the conduct of the study.

9.8 Statistical Analysis Plan

9.8.1 Statistical and Analytical Plans to Address Study Objectives

Refer to [Section 9.8.3](#).

9.8.2 Determination of Sample Size and Power to Address Study Hypotheses

Refer to the protocol [16.1.1.4].

9.8.3 Statistical/Analytical Methods and Issues

Pharmacokinetics

The plasma PK of MK-7264 administered to subjects with varying degrees of RI was compared to healthy matched control subjects using regression and categorical analysis.

Regression Analysis (Part 1)

Separately, individual values of AUC_{0-last}, AUC_{0-∞}, C_{max}, CL/F, and CL_r were ln-transformed and evaluated with a linear fixed-effects model containing eGFR as a continuous variable. The subject's mean renal function value derived from 2 serum creatinine

measurements at screening were used for the analysis. Estimates of the slope and intercept, together with corresponding 95% confidence intervals (CI) were obtained. The estimated mean and corresponding 95% CI for each RI group were predicted at the mid-point of the defined eGFR range for each group (45 mL/min/1.73 m² for moderate and 22.5 mL/min/1.73 m² for severe). Although subjects with mild RI were not enrolled in this study, the PK of MK-7264 were also predicted in this population at the eGFR of 75 mL/min/1.73 m² (the midpoint of the eGFR range for mild RI of 60 - 89 mL/min/1.73 m²). For the healthy population, the estimated mean and corresponding 95% CI were predicted at the median of the observed eGFR values. The predicted means and corresponding 95% CIs were exponentiated to obtain estimates on the original scale. In addition to running the regression analysis using BSA normalized eGFR as the measure of renal function for each subject, the analysis was also run using BSA non-normalized eGFR and CrCL from the Cockcroft-Gault (C-G) equation.

Categorical Analysis (Part 1 and Part 2 Period 1)

Separately, individual values of AUC_{0-last}, AUC_{0-∞}, C_{max}, CL/F, and CL_r were ln-transformed and evaluated with a linear fixed-effects model containing a categorical effect for population (ESRD Non-HD, severe RI, moderate RI, and healthy matched control, based on BSA normalized eGFR). The REPEATED statement with the GROUP=Population option was used in SAS PROC MIXED to estimate separate variances for each population. The Kenward-Roger adjustment was used to calculate the denominator degrees of freedom for the fixed-effect (DDFM=KR). Ninety-five percent (95%) CI for the least-squares means for each population were constructed on the ln-scale and referenced to the t-distribution. The least-squares means (LSM) and their corresponding 95% CI were exponentiated to yield estimates for the population geometric means (GM) and CI about the GM on the original scale. To compare subjects with RI in each of the renal categories to subjects with normal renal function, a two-sided 90% CI for the true difference in means (renal impairment – normal renal function) was calculated for each PK parameter (AUC_{0-last}, AUC_{0-∞}, C_{max}, CL_r, and CL/F) using the mean square error from the model and referencing a t-distribution. For each of the RI populations, these confidence limits were exponentiated to obtain the 90% CI for the true GMR renal impairment/normal renal function) for each PK parameter. Figures showing individual PK values with GMs (95% CI) by population, were provided for AUC_{0-last}, AUC_{0-∞}, C_{max}, CL/F, and CL_r.

ESRD HD vs ESRD Non-HD (Part 2)

To evaluate the extent of MK-7264 removal by HD in Part 2, a linear mixed-effects model with population (ESRD Non-HD, ESRD HD) as a fixed effect was used. An unstructured covariance matrix was used to allow for unequal variances and to model the correlation between the two measurements within each subject via the REPEATED statement in SAS PROC MIXED. The Kenward-Roger adjustment was used to calculate the denominator degrees of freedom for the fixed-effects (DDFM=KR). A ln-transformation was applied to AUC_{0-last}, AUC_{0-∞}, C_{max}, and CL/F. For each PK parameter, 95% CIs for the LSMs was constructed on the ln-scale and referenced the t-distribution. The LSMs and corresponding 95% CIs were then exponentiated to obtain population GM and CI about the GM on the

original scale. A two sided 90% CI for the true difference in means (ESRD HD - ESRD Non-HD) was calculated for each PK parameter (AUC0-last, AUC0- ∞ , Cmax, and CL/F) using the mean square error from the model and referencing a t-distribution. These confidence limits were exponentiated to obtain the 90% CI for the GMR (ESRD HD / ESRD Non-HD) for each PK parameter.

Other Pharmacokinetic Analyses

Subjects with moderate and severe RI and healthy matched control subjects (based on their BSA normalized eGFR) were re-categorized into different renal categories based on their BSA non-normalized eGFR and CrCL. Non-model based summary statistics by population were provided for AUC0-last, AUC0- ∞ , Cmax, CL/F and CLr.

Non-model-based %CV of the GM were presented for plasma MK-7264 AUC0-12, AUC0-24, AUC0-48, apparent terminal $t_{1/2}$, and Vz/F for subjects with moderate and severe RI, ESRD Non-HD, ESRD HD, and healthy matched control subjects. Individual values were also listed for each PK parameter by population and non-model-based descriptive statistics were provided.

Arithmetic mean (AM) concentration-time plots (with and without standard deviation [SD] error bars) of plasma, pre- and post-dialyzer plasma, and dialysate MK-7264 were presented by population on a linear-linear scale plot with an inset semi-log scale plot. The BLQ values were treated as 0 for the calculation of the AM (and SD, as appropriate). At the beginning of the profile, if < 50% of subjects had a quantifiable concentration \geq LLOQ for a given time point, the AM concentration was presented as 0. At the end of the profile when concentrations from some subjects began to fall BLQ, the AM value was only plotted if \geq 50% of subjects had quantifiable concentrations \geq LLOQ and the AM value was \geq LLOQ. However, all AM values were presented in the concentration tables. A reference line for the LLOQ value was added to the plot, where possible, as well as a footnote indicating the AM concentrations at or after certain time points that were not presented since > 50% of subjects had values < LLOQ or the AM was < LLOQ.

AM (with and without SD error bars) cumulative Ae-time plots of urine MK-7264 were presented by population on a linear-linear scale plot. BLQ urine MK-7264 concentration values were treated as 0 for the calculation of the Ae and respective AM (and SD, as appropriate). AM (with and without SD error bars) rr - time (with time corresponding to the midpoint of the 1-minute dialysate collection) plots of urine MK-7264 were presented on a linear-linear scale plot. BLQ MK-7264 concentration values were treated as 0 for the calculation of the rr and respective AM (and SD, as appropriate).

Safety

Safety and tolerability of MK-7264 was evaluated by clinical assessments, including AEs, vital signs, physical examination, 12-lead ECGs, and standard laboratory safety tests (hematology, chemistry, and urinalysis) which were obtained at pre-specified time points throughout the study. AEs were coded according to Version 20.0 of the Medical Dictionary

for Regulatory Activities (MedDRA[®]) as modified by Merck. Incidence of the number of subjects with AEs was tabulated by population. AEs related to study drug were also tabulated by population. AEs were listed by subject. Since no meaningful changes in individual laboratory safety values, ECGs, and vital signs were observed, summary statistics were not provided.

9.8.3.1 Handling of Dropouts or Missing Data

There were no subject discontinuations in this study.

Peripheral blood samples could not be collected at 6 time points (0.25, 3, 3.5, 4.5, 5.5, and 36 hours postdose) for 1 subject with ESRD in Part 2, Period 1, and for 1 time point (16 hours postdose) for the same subject in Part 2, Period 2, due to difficult venipuncture. Therefore, the plasma MK-7264 concentrations at these time points were treated as missing.

Urine samples could not be collected in Periods 1 and 2 of Part 2 for the same 5 of 6 subjects with ESRD. Therefore, urine MK-7264 concentrations at each collection interval were treated as missing.

The dialysate samples at 4 hours postdose for 1 subject and at 4.5 hours postdose for 2 subjects were mistakenly discarded. Therefore, the dialysate MK-7264 concentrations at these time points were treated as missing.

9.8.3.2 Multicenter Studies

This study was conducted at 2 clinical sites. Data from both sites were combined for data summarization and analyses. Study site was not included as a factor in the statistical analyses.

9.8.3.3 Multiple Comparisons/Multiplicity

No hypotheses were tested so no multiplicity adjustment was needed for the study.

9.9 Changes in the Planned Analyses

One (1) subject with ESRD had 6 missing peripheral blood samples (Part 2, Period 1) due to difficult venipuncture. This 1 subject was excluded from the primary PK analyses presented in [Section 11](#). Supplementary analysis including all 6 subjects is shown in [Section 14](#).

One (1) dialysate sample was missing for 3 subjects (4-hour for 1 subject; 4.5-hour for 2 subjects) as they were mistakenly not processed and discarded; therefore, the AD and rr values at these time points could not be determined. In addition, a sensitivity analysis was performed and it was determined that the missing sample had minimal impact ($\leq 1\%$) on the extent of removal of MK-7264 by HD; therefore, a decision was made to include all subjects in the analysis.

Five (5) of the 6 ESRD subjects did not produce urine; therefore, PK parameters in Periods 1 and 2 of Part 2 could not be calculated. Although the remaining subject did produce urine, MK-7264 concentrations in urine were not quantifiable.

For Part 1, the protocol classified the categorical analysis as a secondary analysis; however, when Part 2 was added, it was considered as a part of the primary analysis used to assess the primary PK objective in ESRD subjects, and was described as such in the statistical analysis plan.

The protocol stated that dialysate samples would be collected pre- and post-HD, as well as for 1 minute every half hour during HD; however, as dialysate is a product of HD, no pre- or post-HD samples were obtained.

Non-model based summary statistics by population based on BSA normalized eGFR were provided for both primary (AUC_{0-∞}, AUC_{0-last}, C_{max}, CL/F, and CL_r) and exploratory endpoints (AUC₀₋₁₂, AUC₀₋₂₄, AUC₀₋₄₈, T_{max}, V_{z/F}, apparent terminal t_{1/2}, Ae₀₋₁₂, Ae₁₂₋₂₄, Ae₂₄₋₄₈, Ae₀₋₂₄, Ae₀₋₄₈, Fe₀₋₁₂, Fe₁₂₋₂₄, Fe₂₄₋₄₈, Fe₀₋₂₄ and Fe₀₋₄₈). However, non-model based summary statistics by population based BSA non-normalized eGFR and CrCL using C-G equation were provided only for primary AUC_{0-∞}, AUC_{0-last}, C_{max}, CL/F and CL_r, as some categories had few or no subjects.

There were no other changes to the planned analyses of the original protocol [16.1.1.4].

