Moderate Insufficiency	6	30 – 59 ***																				
Healthy Matched Control	6	≥90****																				
Part 2																						
ESRD requiring HD	6	requiring HD																				

	
Part 2:
 
Subjects with ESRD requiring HD will receive a single dose of MK-7264 on two occasions.
 
On Day 1 of Period 1, subjects with ESRD requiring HD will receive a single oral dose of MK-7264 immediately following their scheduled HD, followed by pharmacokinetic sampling for 72 hours. Subjects will initiate the next HD immediately following the 72-hour blood draw on Day 4. If the next scheduled HD must be initiated before 72 hours postdose, a sample for MK-7264 analysis will be collected prior to HD. Urine samples will be collected for 48 hours postdose, if possible.
 
On Day 1 of Period 2, subjects with ESRD requiring HD will receive a single oral dose of MK-7264 approximately 2 hours prior to their scheduled HD followed by pharmacokinetic sampling for 72 hours. The HD session will initiate immediately following the 2-hour blood draw. During this dialysis session, pre- and post-dialyzer plasma samples will be collected every 30 minutes and dialysate samples will be collected pre-dialysis, post-dialysis, and for 1 minute every 30 minutes during HD for MK-7264 analysis. Urine samples will be collected for 48 hours postdose, if possible.
 
There will be a washout period of approximately 7 days (with 3 dialysis sessions) between MK-7264 dosing in Periods 1 and 2.
 
Both Parts:
 
The clinic will contact all subjects (including those who terminate the study early) approximately 14 days after the last study drug administration to determine if any adverse events have occurred since last visit.

Blinding:	This is an open-label study.
Number of Subjects:	Twenty-four (24), adult, male and female subjects between 18 and 80 years of age (inclusive) will be enrolled; 6 subjects with ESRD requiring HD, 6 subjects with severe RI, 6 subjects with moderate RI, and 6 healthy matched control subjects. Once subjects with severe and moderate RI and subjects with ESRD are enrolled, the healthy matched control subjects will be enrolled. Each healthy control subject will be matched to the mean age (± 10 years) and weight (± 10 kg, where the weight is rounded to the nearest kg) of subjects with RI.

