- m. During HD, blood samples for MK-7264 will be collected from both the pre-dialyzer and post-dialyzer blood lines in addition to peripheral PK blood draw; thus 3 samples per time point during HD will be taken. A blood sample (a pre-dialyzer and post-dialyzer) will also be obtained immediately before the HD is stopped, if this time point does not coincide with a time point that is already scheduled.
- n. Dialysate samples for determination of MK-7264 will be obtained pre-dialysis, post-dialysis (immediately before the HD is stopped), and for 1 minute every half hour during HD.
- o. The HD session will be initiated immediately following the 2-hour postdose blood draw and the HD period will be approximately 4 hours in duration.
- p. To be performed on Day 4 of Period 2 or prior to early termination from the study.
- q. The clinic will contact all subjects (including subjects who terminate early) approximately 14 days after the last study drug administration to determine if any adverse events have occurred since the last study visit.

Abbreviations: C-I = Check-in, CRU = Clinical research unit, DNA = deoxyribonucleic acid, FBR = Future Biomedical Research, FSH = Follicle-stimulating hormone, FU = Follow-Up, HD = Hemodialysis, HIV = Human immunodeficiency virus, IRB/IEC = Institutional review board/independent ethics committee, P = Predose, PK = Pharmacokinetic.

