11.1.3 Hemodialysis: Dialysate and Plasma

For subjects with ESRD only, pharmacokinetic parameters for plasma MK-7264 will be calculated as follows based on concentration in plasma samples from the pre-dialyzer line during the dialysis period (Ca) and on concentration in plasma samples from the post-dialyzer line during the dialysis period (Cv):

AUCD: Plasma AUC values determined from Ca versus time profile during the dialysis period (2-6 hours) using 'linear up, log down' calculation method option in WinNonlin.

AUC(2.5-6)Ca: Plasma AUC values determined from Ca versus time profile during the dialysis period from 2.5 hour to 6 hours using 'linear up, log down' calculation method option in WinNonlin.

AUC(2.5-6)Cv: Plasma AUC values determined from Cv versus time profile during the dialysis period from 2.5 hour to 6 hours using 'linear up, log down' calculation method option in WinNonlin.

CLD,plasma: Dialysis clearance based on plasma, calculated as $Q \times R \times [AUC(2.5-6)Ca - AUC(2.5-6)Cv] / AUC(2.5-6)Ca$, where Q is the flow rate of blood through the dialyzer, and R is the ratio of blood drug concentration to plasma drug concentration

For subjects with ESRD only, pharmacokinetic parameters for dialysate MK-7264 will be calculated as follows:

CD: Concentration in dialysate samples.

AD: Amount of drug recovered from each dialysate collection, calculated as:
 $CD \times \text{dialysate volume}$

rr: Rate of drug removal, calculated as: $(CD \times \text{dialysate flow rate})$

AD, total: Cumulative amount of drug recovered from the dialysate will be obtained by integrating the rr versus time profile over the dialysis session duration, using actual times relative to the start time of dialysis.

CLD,dialysate: HD clearance based on dialysate, calculated as: $AD,\text{total}/AUCD$.

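### Does SAP 9.9 mean the end-of-dialysis dialysate sample was never taken, and would that distort the amount of drug removed?

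*SAP*

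**What the plan says.** In Protocol section 6.2, footnote n, the dialysate samples include one "post-dialysis (immediately before the HD is stopped), and for 1 minute every half hour during HD". The Synopsis and section 9.1 list the same scheme without that gloss: "dialysate samples will be collected pre-dialysis, post-dialysis, and for 1 minute every 30 minutes during HD for MK-7264 analysis". SAP section 9.7 says that one purpose of Amendment 3 was "to clarify that the last post-dialyzer blood sample and dialysate sample were to be collected immediately before HD was stopped", and closes with "There were no other changes in the conduct of the study". SAP section 9.9 then reports that "as dialysate is a product of HD, no pre- or post-HD samples were obtained".

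On missing data, SAP section 9.8.3.1 states: "The dialysate samples at 4 hours postdose for 1 subject and at 4.5 hours postdose for 2 subjects were mistakenly discarded". For these losses SAP 9.9 adds that "a sensitivity analysis was performed and it was determined that the missing sample had minimal impact", quantified as 1% or less.

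Protocol section 11.1.3 defines the removal rate rr as dialysate concentration times dialysate flow. AD,total is "obtained by integrating the rr versus time profile over the dialysis session duration, using actual times relative to the start time of dialysis". CLD,dialysate is AD,total divided by AUCD, the plasma AUC over 2 to 6 h. Section 7.2.3 names these among the measures of removal by HD. Section 8.1.3 lists them as exploratory, and section 11.2.3.3 gives them listings and descriptive statistics only.

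**The concern.** Footnote n's post-dialysis sample is taken with HD still running, so the reason in SAP 9.9, that dialysate exists only because of HD, does not account for its absence. Either a planned sample was not collected, the reason given does not fit, and the closing sentence of SAP 9.7 is incomplete; or it was collected and SAP 9.9 misdescribes the protocol.

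The integral for AD,total covers the whole session. If the half-hourly samples ran only from 2.5 to 5.5 h, both ends of the session would lie outside the sampled span. The check showing an impact of 1% or less concerns interior points, which have neighbors on both sides, so it gives no assurance about the ends. A shortfall in AD,total would pass in full to CLD,dialysate, because AUCD still runs to 6 h. Extent of removal by HD is a primary objective of Part 2 (Protocol section 8.1.1).

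**Working it through.** **1. The wording.** Footnote n and SAP 9.7 say what was planned; SAP 9.9 alone says what was obtained. SAP 9.9 restates the protocol as samples before HD, after HD, and each half hour during HD, and drops the first two because dialysate comes only from HD. That reason fits samples with HD not running and nothing else. On this reading a sample at about 6 h belongs to the half-hourly series: a 4 h session from 2 h has half-hour marks at 2.5, 3, ..., 6 h. Protocol Table 3 counts the last on-HD blood point in a compatible way: 20 scheduled times × 2 periods + 9 on-HD times × 2 extra line samples = 58, and 2, 2.5, ..., 6 h makes nine. That is blood, not dialysate, so it supports this reading without proving it.

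**2. The plan's own figure (1% or less).** Assume rr(t) = exp(−kt) for t = 0 to 4 h of HD. The documents give no rate on HD. A flat or falling rr is reasonable because Protocol section 9.2.3 equates 3 h with twice Tmax, so Tmax is about 1.5 h and HD starts after it. The 1.4 to 1.5-fold twice-daily accumulation in section 7.2.2 implies k = ln[R/(R−1)]/12 = 0.104 to 0.092/h, but off HD and not in ESRD. I use k = 0 to 0.35/h. Dropping the 4 h point and joining its neighbors linearly changes the integral by 0.5 × exp(−2k) × [cosh(0.5k) − 1]. At k = 0.35 this is 0.5 × 0.4966 × 0.01535 = 0.0038, against a total of (1 − e^−1.4)/0.35 = 2.153, or 0.18%. The reported figure is consistent with this.

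**3. Share of AD,total in each end interval.** First half hour: (1 − e^−0.5k)/(1 − e^−4k). Last half hour: (e^−3.5k − e^−4k)/(1 − e^−4k).

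| k (/h) | First 0.5 h | Last 0.5 h | Sum |
|---|---|---|---|
| 0 | 12.5% | 12.5% | 25.0% |
| 0.1 | 14.8% | 10.4% | 25.2% |
| 0.2 | 17.3% | 8.6% | 25.9% |
| 0.35 | 21.3% | 6.3% | 27.6% |

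Only the last half hour depends on the 6 h sample. The first half hour lacks a start value whether or not that sample exists. A true pre-dialysis dialysate sample would contain no drug and could not supply one. For the last half hour alone to hold 25%, rr would have to double about every 1.4 h during HD.

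**4. Error when the full session is integrated.** Carry the nearest sample to the end of the session, with a log-down trapezoid between samples:

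| k (/h) | 6 h sample taken (first 0.5 h filled) | 6 h sample lost (both ends filled) | Difference due to the 6 h sample |
|---|---|---|---|
| 0 | 0 | 0 | 0 |
| 0.1 | −0.37% | −0.10% | +0.3% |
| 0.2 | −0.85% | −0.41% | +0.4% |
| 0.35 | −1.81% | −1.25% | +0.6% |

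At k = 0.35 the last half hour is truly (0.2938 − 0.2466)/0.35 = 0.1347. Carrying the 5.5 h value forward gives 0.5 × 0.2938 = 0.1469. The difference, 0.0121, is 0.56% of 2.153. Log-linear extrapolation gives 0 to +0.3% overall.

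**5. What a large error would require.** Setting rr to zero at the unsampled ends gives −12.5% to −14.4% if the 6 h sample was lost and −6.25% to −11.6% if it was taken. Stopping the integral at 5.5 h loses the last-half-hour share, 6.3% to 12.5%. The first is stated nowhere: SAP 9.8.3 applies zero to values below the quantification limit, and 9.8.3.1 treats uncollected dialysate concentrations as missing. The second departs from the definition of AD,total.

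**The case for a change.** The strongest case for acting is that the documents do not settle what was collected. The list of lost samples in SAP 9.8.3.1 omits any 6 h loss, but it also omits the planned pre-dialysis sample that 9.9 says was never obtained, so its silence proves little. No section states how the ends of the session were filled, and the first half hour needs a fill on either reading. The sensitivity check does not reach the ends. A few sentences and one recalculation would close the matter.

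Much of this stands as description: the wording in 9.9 is loose, and the fill is not written down in these documents. It does not stand as a reason for change. The figure of about 25% unsampled is a share, not an error, and about half or more of it has nothing to do with the 6 h sample. With one-minute collections each half hour, nearly all of AD,total is interpolated by design. SAP 9.9 names the 4 h and 4.5 h samples and claims nothing about the ends. Either ordinary fill keeps the error to about 2% or less, whichever reading is true.

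**Conclusion.** The conflict in wording is real but clerical, and the missing fill rule is one that analysts following the definition in Protocol section 11.1.3 would supply sensibly. If the 6 h sample was not taken, the half hour it bounds holds about 6% to 12.5% of AD,total. Filling that half hour by carrying the 5.5 h value forward changes AD,total, and CLD,dialysate with it, by 0 to +0.6%. Total error with the session ends filled runs from about −1.8% to +0.3% across the two fills and both readings.

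This rests on a 4 h session, a half-hour grid, and a flat or declining rr at up to 0.35/h. A faster decline would enlarge the carry-back error in the first half hour, but that interval does not depend on the disputed sample. The figures are illustrations, not bounds, because no rr data are given.

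The affected parameters are descriptive. The Period 2 to Period 1 geometric mean ratios come from plasma, and CLD,plasma comes from the pre- and post-dialyzer lines over 2.5 to 6 h, so none of these moves. No result or conclusion would change, and no change to the plan is needed.
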